rTMS. Furthermore, it is well known that in order to derive a meaningful clinical effect, the application of multiple sessions of rTMS are needed. 2: This will be the first trial testing an accelerated rTMS treatment paradigm using established rTMS doses in an addictions population. This is important as there is a clear dose response effect in rTMS, where larger doses of rTMS result in a larger clinical effect ([name] et al., 2010; McDonald et al., 2011). It is additionally important as OUD and other substance use disordered populations may be difficult to treat using the standard treatment paradigm of one session per day over several weeks. 3: This trial will be the first to use rTMS as an adjunct to standard of care opioid treatment. OUD patients, including Veterans, are difficult to engage in outpatient care. Subsequently, a treatment that encourages retention and integration early in the recovery process could have a significant impact on patient outcomes.

RESEARCH DESIGN AND METHODS

Approach Overview (Figure 3): Participants will be recruited from the Ralph H. Johnson VAMC, local VA clinics, and Charleston Center. We will collect data at one week, four weeks, and three months following rTMS completion.

[figure not shown]
Acute Phase: We will screen, consent, enroll, and assess participants during an enrollment session. Following enrollment, each participant will complete baseline measurements of opioid use, opioid craving, pain, and functioning (as outlined below). Following the enrollment session, each participant will be randomized and begin the acute treatment phase of the trial. *Participants will receive a total of six sessions of rTMS on three days during the acute phase of the study over a period of up to three weeks. A period of up to one-week in between treatment days will be allowed to maximize feasibility of intervention deliverability in this population while minimizing risk of a treatment gap that is too long to allow for a summation of effect.* On the third treatment day, pain assessments will be repeated. Craving and pain will be assessed using validated questionnaires.

Continuation Phase: Participants will return at one week, four weeks, and three months for follow-up visits to preliminarily assess the intervention's impact on opioid use, pain, and functional outcomes.

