rTMS Treatments: rTMS will be delivered via a MagPro double blinded rTMS Research System (MagVenture, Denmark) with a Cool-B65 Butterfly Coil (a combined active and sham coil). We will use a standard resting motor threshold (rMT) determination to determine the TMS dose ([name] et al., 2006). Treatment will be delivered at 120% rMT. Each active rTMS treatment will consist of a total of 600 pulses of 50 Hz triplets for 2s, and repeated every 10s for a total of 190s of stimulation. Treatments will be delivered at the EEG coordinate for F3 (approximating the left DLPFC), and will be found using the Beam-F3 method (Beam et al., 2009). This is a treatment paradigm that has been used extensively in other trials ([name] et al., 2008; Short et al., 2011; [name] et al., 2014; Li et al., 2013). Sham sessions will be delivered using an electronic sham system consisting of a coil that mimics the appearance and sound of TMS, combined with a TENS device which produces a small electric shock mimicking the feeling of real rTMS. This type of sham has been demonstrated to be indistinguishable from real rTMS, has been well tolerated ([name] et al., 2010; [name] et al., 2014) and successfully used in other clinical trials ([name] et al., 2008; Arana et al., 2008). During each session of rTMS we will present a series of opioid related images, including those utilized in previous studies (Garland et al., 2015; Garland & Howard, 2014). The application of drug cues during rTMS appears to enhance its efficacy (Dinur-Klein et al., 2014). Opiate craving and stress will be assessed before and after each TMS treatment.

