Statistical Analysis: *Study feasibility will be primarily measured by a) the total number of rTMS sessions completed (out of 18 total sessions) b) the proportion of participants completing all of the rTMS session and c) the proportion of participants completing all of the rTMS sessions as well as the follow-up visits. Study tolerability will be measured as the total number of treatment emergent adverse events. Group differences (active rTMS vs. sham rTMS) in the feasibility and tolerability measures will be estimated using generalized linear models with appropriate distributions (Negative binomial for session and AE count and logit for study treatment completion). In addition to study feasibility, efficacy measures (opioid use amounts, pain, and sleep quality) will be estimated for the entire cohort as well as estimates of between group differences. Changes in study efficacy outcomes from baseline to follow-up visits will be estimated and analyzed using appropriate statistical approaches. When parametric modeling assumptions can be made, changes over time and associated variability will be estimated between treatment groups using general linear mixed models (GLMMs). The GLMMs will allow us to estimate group-specific changes over time and overall effect sizes, along with the variation in those measures, while controlling for relevant baseline covariates (e.g. baseline craving, morphine equivalents, withdrawal). Although we will likely not be powered to detect between-group differences in binary outcomes (i.e. any drug use), such effects will be explored using generalized mixed models, and for time-to-event data (e.g. days to first opioid use), survival analysis models will be constructed. When parametric modeling assumptions do not appear to be valid, alternative (e.g. non-parametric) approaches will be used. Efficacy outcomes will also be analyzed for evidence of differential treatment effects in subgroups determined by gender, race, and ethnicity. Post-hoc exploratory analyses using GLMMs within the active rTMS group will address whether specific characteristics (e.g. demographics, baseline craving, morphine equivalents, withdrawal, PTSD) are associated with a differential treatment effect. The subgroup-specific treatment effects and corresponding confidence intervals will be constructed and will be interpreted in terms of their clinical, rather than statistical, significance, and effect size of treatment to inform future trials will be estimated.* **Missing Data and Attrition:** *Missing data in longitudinal studies can be a problematic feature but can be mitigated through study design considerations. We will make every effort to prevent attrition, e.g., telephone/text/e-mail reminders prior to visits, and reinforcing attendance at each visit. However, these methods do not ensure that all data will be collected, and appropriate analysis methods will be employed to accommodate missing data. Maximum likelihood estimation yields valid inferences assuming ignorable attrition (i.e., attrition is accounted for by covariates or the dependent variable measured prior to dropout). In addition, in keeping with the ITT, we will make every effort to continue assessments for the entire course of randomized treatment, even among those who stop participating in the study assigned intervention or fail to complete the full rTMS time course.*

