
Sample Size Justification: A total of n=20 participants (n=10 per arm) will be enrolled. We anticipate that <20% of study participants will withdraw from the study or be lost to follow-up, meaning that $\geq n=16$ participants are expected to complete the study. This sample size should allow us to assess feasibility and tolerability of the intervention, and ensure that group-specific changes will be able to be estimated in a precise fashion, with 95% confidence intervals extending ~ 0.5 standard deviation units. Similarly, the overall effect size confidence interval

will likely extend only 0.3 standard deviation units. As an exploratory and developmental project, we recognize that our final sample size will not result in a fully powered study design. Model based means and variability estimates will be derived from unadjusted and adjusted analyses and will be vital for designing a larger, more definitive trial in the context of a subsequent MERIT submission. **Relapse, Drop-Out and Clinical Deterioration:** Every effort will be made to re-engage participants who miss appointments. Clinical deterioration, such as exacerbation of psychiatric or substance use disorders, will be assessed on a case-by-case basis and appropriate care will be arranged. In the case of suicidal ideation, standard STAR program operating procedures will be followed which entails contact of on-call STAR clinicians. Participants will be considered drop outs if they do not come back for follow-up visits after three attempts to contact. With the exception of participants who formally withdraw from the study, we will attempt to assess early terminators at the time of discontinuation and at the post-treatment time points. These participants will be considered in the intent-to-treat efficacy analyses.

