Design Considerations: *Choice of treating participants likely undergoing buprenorphine treatment and using an accelerated (multiple sessions per day) treatment paradigm:* The standard rTMS treatment paradigm in depression is to treat outpatients using one session of rTMS each day, five times per week, for four to six weeks. We considered using this treatment paradigm; however, we chose to use an accelerated paradigm (multiple sessions per day), for the following reasons: 1: If treating outpatients with once daily sessions, there would likely be a great deal of variability in the number of attended sessions per week (OUD patients frequently miss appointments) and a large attrition rate (the opioid relapse rate is high amongst outpatients). 2: Patients are often seen frequently early in treatment (leaving an opportunity for an acute intervention that could easily be applied in other facilities). 3: Our preliminary evidence suggests that rTMS is tolerated while participants are on buprenorphine. *Choice of including participants with co-morbid depressive symptoms:* Because rTMS is known to have an anti-depressant effect we considered excluding patients with concurrent depressive symptoms to avoid the potential confound of improved depression driving anti-pain and anti-craving effects. We chose to include these patients as there is a high rate of comorbid depression in this population (Gros et al., 2013), and excluding these patients would reduce the generalizability of our findings. We will control for depression statistically by including depression as a covariate in analyses. *Consideration of gender as a biological variable:* Though this trial is not powered to detect gender differences, we will perform our analysis using gender as a potential covariate.

Operational Plan and Research Timetable: Funding for two years is requested. The first three months will be used for submitting regulatory documents, staff training and preparing for study initiation. Eighteen months will be needed for patient recruitment and data collection. The final three months will be used for data analysis, dissemination, and MERIT grant submission. At a recruitment rate of approximately 1-2 participants per month, we should have no difficulty in completing the study in the proposed timeframe.

PROTECTION OF HUMAN SUBJECTS

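### The efficacy models work on change from baseline without naming the outcome's own baseline as a covariate, which may widen the active-sham interval, and withdrawal is a planned covariate with no named measure

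*Combined protocol and SAP*

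**What the plan says.** The Statistical Analysis section lists "efficacy measures (opioid use amounts, pain, and sleep quality" as the efficacy measures and continues: "Changes in study efficacy outcomes from baseline to follow-up visits will be estimated and analyzed using appropriate statistical approaches". Where parametric assumptions hold, mixed models are to estimate change over time by arm, "while controlling for relevant baseline covariates (e.g. baseline craving, morphine equivalents, withdrawal". The same section lists withdrawal again among the characteristics to be explored as modifiers of the treatment effect within the active arm.

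Design Considerations adds a firm commitment, "We will control for depression statistically by including depression as a covariate in analyses", and a looser one, "we will perform our analysis using gender as a potential covariate". Sample Size Justification states that "Model based means and variability estimates will be derived from unadjusted and adjusted analyses".

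No section says whether the outcome's baseline enters as a subtraction, as one of the repeated responses or as a covariate. Treatment Assignment stratifies on concomitant pain medication (yes/no), and no section carries that factor into a model.

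Table 1 schedules the pain diaries, Brief Pain Inventory, McGill, PSQI and Timeline Follow-Back at screening. The Acute Phase text describes "baseline measurements of opioid use, opioid craving, pain, and functioning". Craving has no row in Table 1 but is collected: "Opiate craving and stress will be assessed before and after each TMS treatment". Neither the table nor the text names an instrument for withdrawal.

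**The concern.** The baseline of the outcome itself is usually the strongest predictor of its follow-up value. It is already collected here and costs one degree of freedom. The plan instead names other variables as examples.

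A contrast built on change alone carries part of any chance baseline imbalance into the treatment estimate. With 10 per arm, the baseline difference between arms has a standard error of sqrt(2/10) = 0.45 SD. A change score passes on (1 - rho) of that difference, where rho is the baseline to follow-up correlation.

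This matters because the trial is meant to supply means and variability for planning a larger one, and because 16 to 20 people leave little room for a poorly chosen covariate set. The withdrawal problem is of a different kind: two planned analyses use a variable that the documents give no means of measuring.

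**Working it through.** **Inputs from the documents.** 20 enrolled, 10 per arm, and at least 16 completers (Sample Size Justification). I take 16 completers as 8 per arm.

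**Assumptions.** rho from 0.3 to 0.8 (not stated in the documents), one follow-up visit, equal SDs, and results in units of the raw outcome SD.

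**The plan's own precision figure.** Sample Size Justification gives about 0.5 SD for a group-specific change. The one-sample half-width t(n-1)/sqrt(n) is 2.262/sqrt(10) = 0.72 at n = 10 and 0.84 at n = 8, so 0.5 does not reproduce directly. Read as a change score in raw SD units, with SD sqrt(2(1 - rho)), it needs rho = 0.76 (n = 10) or 0.82 (n = 8). The plan states neither that reading nor a correlation. The precision statement is a separate issue.

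**Step 1: residual variance at one visit.** Change score: 2(1 - rho). Own baseline as covariate: 1 - rho^2. The difference is (1 - rho)^2, which is the baseline imbalance that the change score lets through.

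**Step 2: half-width of the active-sham interval.**
- Change score: t(N-2) x sqrt(2(1 - rho) x 2/n), with n per arm.
- Own baseline: t(N-3) x sqrt((1 - rho^2) x 2/n x (N-3)/(N-4)). The last factor is the expected cost of estimating one slope.

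At rho = 0.5 and N = 16:
- Change score: 2.145 x sqrt(1 x 0.25) = 1.07.
- Own baseline: 2.160 x sqrt(0.75 x 0.25 x 13/12) = 0.97.
- Ratio: 1.10.

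| rho | N=16: change, own baseline | excess | N=20: change, own baseline | excess |
|---|---|---|---|---|
| 0.3 | 1.27, 1.07 | 18% | 1.11, 0.93 | 20% |
| 0.5 | 1.07, 0.97 | 10% | 0.94, 0.84 | 12% |
| 0.7 | 0.83, 0.80 | 3% | 0.73, 0.69 | 5% |
| 0.8 | 0.68, 0.67 | 0.5% | 0.59, 0.58 | 2% |

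Simulation of change-score and own-baseline regressions (4,000 runs per setting, rho 0.3, 0.5 and 0.7) gave the same pattern, with half-widths slightly below these.

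**Step 3: cost of further covariates.** In a regression with one row per person, k covariates that explain nothing widen the interval by an expected sqrt((N-3)/(N-3-k)) x t(N-2-k)/t(N-2). For three (craving, morphine equivalents, depression):
- N = 16: sqrt(13/10) x 2.201/2.145 = 1.17.
- N = 20: sqrt(17/14) x 2.131/2.101 = 1.12.

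If baseline is one of the repeated responses and the covariates enter only as main effects, this penalty largely disappears, because such terms hardly touch the contrast in change.

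**Step 4: withdrawal.** The word appears in the background, in the two analysis roles described above, and in the seizure-risk text, which concerns withdrawal from alcohol or benzodiazepines. None of these is a measurement.

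**The case against.** The strongest reply is that the plan does not exclude own baseline. The covariates are examples, gender is only potential, unadjusted estimates are also promised, and baseline morphine equivalents may already act as the own-baseline term for opioid use. Baseline is not ignored either, since the plan works on change. If the mixed model takes baseline as a response with a common mean across arms, essentially nothing is lost. All of this stands, and it makes the finding conditional. It does not remove it: nothing comparable is named for pain or sleep, the common mean is not specified, and an unadjusted analysis does not supply the adjustment.

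A reader might infer more than the documents support:

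- **That the interval is necessarily too wide.** No model is fixed, and at rho = 0.8 the difference is close to nil. The correlations of 0.76 to 0.82 implied by one reading of the 0.5 SD figure would put the gain at the low end.
- **That five covariates consume 5 of 14 degrees of freedom and widen the interval by 1.34.** That count includes withdrawal, which cannot be used as written, and gender, which is only potential. It also assumes one row per person.
- **That own baseline is worth 33% more participants at no cost.** That is the large-sample figure at rho = 0.5. Net of the baseline term, squaring the width ratios gives about 21% (N = 16) to 24% (N = 20).
- **That unmeasured withdrawal widens the interval.** It does not. It leaves an analysis that cannot be run.
- **That withdrawal is certainly not collected.** Table 1 is not exhaustive, as craving shows. The supportable statement is that no measure is named.

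**Conclusion.** The point holds as a conditional one. If the contrast is a change score, or comes from a mixed model with separate baseline means, own-baseline adjustment would give a tighter active-sham interval from data already collected. The benefit is moderate at low correlation and negligible at 0.8. It rests on an assumed rho, a single visit, equal SDs and 8 to 10 per arm. Feasibility is the primary measure and the study is openly not fully powered, so this is an improvement to the secondary estimates and does not threaten the trial's main aim. The withdrawal gap needs no assumption about correlation: as written, neither its use as an adjuster nor its use as an effect modifier can be carried out.

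**What to change.** For each continuous efficacy outcome, specify one main model: arm, visit, arm-by-visit, that outcome's own baseline as a covariate (or baseline as a response with a common mean across arms), and the stratification factor, concomitant pain medication yes/no. Keep depression in the adjusted model, as Design Considerations commits. Limit craving, morphine equivalents and gender to sensitivity models. Remove withdrawal from both the adjustment and the effect-modifier analysis, or name the measure if one is collected.

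The cost is analysis-plan wording. Own baseline uses at most one degree of freedom, already netted off in the table. In a one-row-per-person regression the stratification factor uses one more. By the Step 3 formula, going from k = 1 to k = 2 adds at most about 5% at N = 16 (1.104/1.048) and 4% at N = 20 (1.074/1.035) if the factor explains nothing. The cost should be less in practice, because stratification keeps the arms near balance on it.

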Screening and Eligibility Assessment: Individuals will be screened by the research study intake coordinator. An initial pre-screen focused on inclusion/exclusion psychiatric diagnoses, medical status, current medication regimen, and ability and willingness to commit to completion of study procedures will be used to initially determine potential study eligibility. Interested individuals will be given a full description of the study procedures and asked to read and sign an IRB-approved informed consent form before participating in a detailed, comprehensive screening and assessment phase. To ensure subjects are not experiencing any acute effects of alcohol, individuals whose breath or saliva alcohol concentration reading exceeds the instruments margin of error (0.002%) will not be allowed to participate until their BAC is not detectable.

Diagnostic/Descriptive Assessment: The *M.I.N.I. International Neuropsychiatric Interview 7.0 for DSM 5* will be used to assess psychiatric and substance use diagnoses, including assessment of opiate use. A medical history will be collected to ensure that the individual is eligible to participate, and the VA medical record may be reviewed to verify medications. In the event that an individual is found to be ineligible, he or she will be given an appropriate referral for further medical or other necessary care. If the individual is eligible, he or she will fill out questionnaires and provide a urine sample to verify self-report of substance use. If female, the urine will first be tested for pregnancy. If the pregnancy test is negative or the individual is male, the urine will be tested for drugs of abuse. A randomization/initial rTMS visit will be scheduled.

Figure 3

rTMS=Repetitive Transcranial Magnetic

Treatment Assignment: Eligible individuals will be randomized to receive active rTMS or sham treatment. Participants will be randomized using a stratified permuted random block design with block sizes of 2 and 4; *this will be utilized to maintain treatment assignment balance throughout the treatment enrollment period based on concomitant pain medication use (yes/no).*

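### The post-hoc moderator analysis uses the active arm alone, so it cannot estimate the differential treatment effect it names

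*Combined protocol and SAP*

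**What the plan says.** The combined protocol and SAP, under Statistical Analysis, plans this analysis in one sentence, which opens: "Post-hoc exploratory analyses using GLMMs within the active rTMS group will address whether specific characteristics". The examples it gives are "e.g. demographics, baseline craving, morphine equivalents, withdrawal, PTSD". The question put to the model is whether any of these "are associated with a differential treatment effect". No sham comparison and no treatment-by-characteristic term is specified for it.

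Three neighbouring statements bear on it:

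- The two-arm efficacy models estimate change over time "while controlling for relevant baseline covariates (e.g. baseline craving, morphine equivalents, withdrawal"). Three of the five listed characteristics are therefore already adjustment covariates.
- A separate analysis looks for "differential treatment effects in subgroups determined by gender, race, and ethnicity". It is not limited to one arm and is not criticised here. It overlaps the list above only on demographics.
- The sentence that follows promises treatment effects by subgroup with confidence intervals, to be read for clinical rather than statistical importance. The section also says effect sizes will be estimated to inform later trials.

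A concurrent control exists. Under Treatment Assignment, "Eligible individuals will be randomized to receive active rTMS or sham treatment". Sample Size Justification sets 10 per arm and expects at least 16 completers.

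**The concern.** The analysis set and the stated question do not match. An active-only model shows which treated participants changed more. They may have changed more because rTMS worked better in them. They may equally have been going to change more anyway, through prognosis, sham response or the natural course under continuing medication assisted treatment.

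The documents give reason to think prognosis matters. Baseline craving, morphine equivalents and withdrawal are named as relevant covariates for the outcome models. For PTSD, Background and Significance describes poorer engagement and retention in treatment and impaired recovery from opioid use disorder, whatever rTMS does.

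At stake is how a secondary result is labelled. A prognostic factor could be carried into the next trial as a marker of who responds to rTMS, or a real marker could be missed. Confidence intervals would show sampling noise but not this bias.

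**Working it through.** **What each model estimates.** For a characteristic X, let mean change be

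- sham: a + bX
- active: a + t + (b + g)X

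Here b is prognosis shared by both arms, t the treatment effect at X = 0, and g the differential treatment effect. The active-only slope is b + g. The treatment-by-characteristic interaction across both arms is (b + g) − b = g. No increase in sample size makes b + g converge to g unless b = 0.

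The error runs both ways:

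- With b = 0.8 SD and g = 0, the active-only estimate is 0.80 SD and the interaction 0.00.
- With b = −0.8 and g = +0.8 SD, the active-only estimate is 0.00 and the interaction 0.80, so real modification is hidden.

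**Inputs.** Ten per arm and at least 16 completers are from Sample Size Justification; 8 per arm assumes that the completers split evenly. The plan states no figure to reproduce for this analysis, and everything else below is assumed.

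**How often the active-only model misleads when g = 0.** I simulated normal data with one change score per participant (SD 1), least squares, and at least 40,000 runs per setting. X correlates r with change equally in both arms.

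| r | Mean active-only slope (SD per SD) | Active-only 95% CI excludes 0, n = 10 | n = 8 | Two-arm interaction CI excludes 0 |
|---|---|---|---|---|
| 0.1 | 0.10 | about 6% | about 6% | about 5% |
| 0.2 | 0.20 | about 9% | about 7% | about 5% |
| 0.3 | 0.30 | 13% | 11% | about 5% |
| 0.5 | 0.50 | 33% | 25% | about 5% |
| 0.7 | 0.70 | 68% | 55% | about 5% |

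The interaction estimate averages zero in every row.

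**Regression to the mean.** This adds to the problem only where the characteristic is, or correlates with, the outcome's own baseline. An example is morphine equivalents, if opioid use amounts are expressed in those units, which the plan does not say. With test-retest correlation ρ and no treatment effect, corr(baseline, change) = −√((1 − ρ)/2). For ρ = 0.3, 0.5 and 0.7 this gives −0.59, −0.50 and −0.39. The active-only interval then excludes zero in about 47%, 33% and 20% of trials at n = 10.

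**Precision.** For a characteristic split 50:50, with SD of change 1:

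- Active only: t(0.975, n − 2) × √(2/(n/2)). At n = 10, 2.306 × √0.4 = 1.46 SD. At n = 8, 2.447 × √0.5 = 1.73 SD.
- Interaction: t(0.975, 2n − 4) × √(4/(n/2)). At 10 per arm, 2.120 × √0.8 = 1.90 SD. At 8 per arm, 2.179 × √1 = 2.18 SD.
- Power for a 1 SD interaction (noncentral t): 18% at 10 per arm and 15% at 8 per arm.

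**The case against.** The best defence is about weight. The analysis is labelled post-hoc and exploratory, in a 20-person pilot that says it is not fully powered. Results are to be read clinically, so counts of intervals excluding zero are not the plan's own yardstick. Being listed as a covariate does not prove a variable is prognostic, because it may be there to handle chance imbalance. With weak prognosis the false signal is small, as the first two rows of the table show. The regression-to-the-mean case depends on an outcome unit the plan leaves open. Demographics are partly covered by the two-arm subgroup analysis.

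Nor is the interaction always closer to the truth at this size. With normal X and g = 0, the mean squared error is r² + (1 − r²)/(n − 3) for the active-only slope and 2(1 − r²)/(n − 3) for the interaction. At r = 0.3 these are 0.22 and 0.26 for n = 10, and 0.27 and 0.36 for n = 8. At r = 0.5 the order reverses: 0.36 and 0.21 for n = 10, and 0.40 and 0.30 for n = 8.

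All of this stands as a limit on size and on what the fix can deliver. It does not rescue the stated aim. An exploratory label excuses imprecision, but not reporting one quantity under the name of another. Reading the result clinically puts more reliance on the point estimate, which is the part that is biased. Nothing else in the plan supplies a sham contrast for craving, morphine equivalents, withdrawal or PTSD.

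**Conclusion.** The concern holds. As written, the analysis cannot deliver a differential treatment effect, because it estimates b + g and has no means of removing b. That conclusion is algebraic and needs no assumed values.

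Its practical size does depend on assumptions. The bias equals whatever prognostic slope both arms share: 0.3 to 0.7 SD per SD over the main range examined, and close to nothing if the characteristic is barely prognostic. The documents do not say where the true values lie, and the simulation uses one change score where the plan uses repeated visits.

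The sentence should be corrected, but the fault is confined to a secondary exploratory analysis.

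**What to change.** Replace the sentence with: *Post-hoc exploratory GLMMs in all randomised participants will include treatment, the characteristic, time and their interactions; the treatment-by-characteristic (by time) estimate and its 95% CI will be reported as estimation only.*

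If the active-only model is kept, call it *predictors of change under active rTMS* and do not describe its results as a differential treatment effect.

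The cost is one sentence. No new data are needed, since the assessment schedule in Table 1 makes no distinction by arm. The price is precision: for an evenly split characteristic the interval widens from about ±1.5 to ±1.9 SD at 10 per arm, and from about ±1.7 to ±2.2 SD at 8 per arm. The plan should say in advance that such intervals can rule out little.

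### The 95% CI extents of about 0.5 and 0.3 SD in the sample size justification do not follow from 10 per arm, and 0.3 SD cannot be the active-sham precision (minor)

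*Combined protocol and SAP*

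**What the plan says.** The Sample Size Justification section fixes the size of the trial: "A total of n=20 participants (n=10 per arm) will be enrolled". It expects fewer than 20% to be lost, so at least 16 completers. It then makes two numerical statements about precision. Group-specific changes will be estimated "with 95% confidence intervals extending ~ 0.5 standard deviation units". The next sentence begins "Similarly, the overall effect size confidence interval" and says that this interval "will likely extend only 0.3 standard deviation units".

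That section does not say which SD is the unit, whether the extent is a half-width or a full width, which outcome or visit is meant, what correlation is assumed, or what overall refers to.

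The Statistical Analysis section gives some context without linking it to the two figures. Efficacy measures "will be estimated for the entire cohort as well as estimates of between group differences". General linear mixed models are to "estimate group-specific changes over time and overall effect sizes", "while controlling for relevant baseline covariates (e.g. baseline craving, morphine equivalents, withdrawal" among others. The Approach Overview lists follow-up at one week, four weeks and three months.

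**The concern.** These two figures are the only numerical precision claims behind the choice of 20 participants. A reader who tries to reproduce them from the sample size gets clearly wider intervals.

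The second figure is also easy to misread. In a randomised sham-controlled trial, an overall effect size with an interval extending only 0.3 SD can be taken as the precision of the treatment effect. The Statistical Analysis section plans between-group estimates and intends the treatment effect size to inform later trials. A reader who takes 0.3 that way will expect far more from the active-sham comparison than 10 per arm can give.

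**Working it through.** **Inputs.** From the Sample Size Justification: 10 per arm enrolled; at least 16 completers, so 8 per arm if losses are equal; 95% confidence; stated extents 0.5 and 0.3 SD. The documents give no correlation, so every ρ below is an assumption. Both extents are read as half-widths, the reading kinder to the plan; as full widths the shortfall would be larger.

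**1. Can the stated figures be reproduced from n?** Take the SD of the change score as the unit and a common variance with df = 2n − 2, so t(18) = 2.101 and t(14) = 2.145.

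| Quantity | Formula | 10 per arm | 8 per arm | Plan |
|---|---|---|---|---|
| Change in one arm | t/√n | 2.101/√10 = 0.66 | 2.145/√8 = 0.76 | about 0.5 |
| Change in pooled cohort | t/√(2n) | 2.101/√20 = 0.47 | 2.145/√16 = 0.54 | 0.3, if this is meant |
| Active minus sham | t·√(2/n) | 2.101·√0.2 = 0.94 | 2.145·√0.25 = 1.07 | 0.3, if this is meant |

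The per-arm values are 33% to 52% above 0.5. The pooled values are 1.6 to 1.8 times 0.3. The choice of critical value does not change the conclusion: the normal quantile gives 0.62 (0.69) per arm, and each arm's own variance gives 0.72 (0.84). The only direct match to 0.5 is 1.96/√16 = 0.49, which uses all completers and not one arm.

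**2. Is there a set of assumptions that gives the pair?** Change the unit to the raw-score SD. With equal variances before and after, the SD of a simple change is √(2(1 − ρ)) raw SDs. For the mean of three follow-ups adjusted for the outcome's own baseline, with all correlations equal to ρ, the factor is √((1 + 2ρ)/3 − ρ²), with df = 2n − 3. Ranges run over 10 to 8 per arm, and in the last row also over ρ.

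| Assumption | Per arm | Pooled | Active minus sham |
|---|---|---|---|
| Simple change, ρ = 0.75 (factor 0.707) | 0.47–0.54 | 0.33–0.38 | 0.66–0.76 |
| Simple change, ρ = 0.80 (factor 0.632) | 0.42–0.48 | 0.30–0.34 | 0.59–0.68 |
| Three-visit adjusted mean, ρ = 0.3–0.6 (factors 0.666–0.611) | 0.41–0.51 | 0.29–0.36 | 0.58–0.72 |

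The pair 0.5 and 0.3 is therefore roughly reachable when overall means both arms pooled. It is not reached by the active-sham column.

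**3. Can 0.3 be active versus sham while each arm is about 0.5?** The arms are independent, so SE(difference)² = SE(active)² + SE(sham)². There are three cases.

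- Same model, common variance and same df for both intervals: 0.5·√2 = 0.71 between arms. Conversely, 0.3 between arms implies 0.3/√2 = 0.21 per arm.
- Each arm's interval uses its own variance (df 9 or 7), the contrast a common one (df 18 or 14): the ratio is √2·2.101/2.262 = 1.31, or √2·2.145/2.365 = 1.28. So 0.5 implies 0.66 or 0.64.
- Each arm's interval is for a single-visit change and the contrast is the baseline-adjusted three-visit mean. A per-arm 0.5 needs ρ = 0.68 to 0.76 (10 per arm) or 0.74 to 0.82 (8 per arm). Putting these ρ into the three-visit factor gives 0.45 to 0.57 between arms, across normal and t quantiles.

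The lowest value, 0.45, is 1.5 times 0.3; the highest, 0.71, is 2.4 times. For simple change, an active-sham half-width of 0.3 would need ρ of about 0.95 to 0.96, and each arm would then be about 0.21.

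**4. Sample size for an active-sham half-width of 0.3.** The smallest n with t·√(2/n)·factor ≤ 0.3 is 87 per arm for factor 1 (SD-of-change units). It is 44, 40, 36 and 34 per arm for factors 0.707, 0.666, 0.632 and 0.611.

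**The case against.** The strongest reply is that the plan never says that 0.3 is the active-sham precision. It sets group-specific changes against something overall, and the Statistical Analysis section does plan estimates for the whole cohort. On that reading 0.5/√2 = 0.35, close to the stated 0.3. This stands. A reader might infer that 0.3 is a proven arithmetic error; the documents do not support that, because a pooled-cohort reading in raw-score SDs roughly fits.

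A second reply is that 0.71 is not general. This also stands: it requires both intervals to share model, variance estimate and df. Mixed models with baseline covariates and three follow-ups make a mixed basis plausible, and that brings the active-sham figure down to about 0.45. It does not bring it to 0.3.

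Third, a reader might infer that the plan names no model or target quantity at all. That goes too far. It names group-specific changes and mixed models, and it says "Model based means and variability estimates will be derived from unadjusted and adjusted analyses". What is missing is any link from these to 0.5 and 0.3.

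Fourth, the change-score values in the first table are not the planned analysis, which has repeated visits and covariates. This is fair, and any such values must be labelled accordingly.

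Finally, the consequences are small. Feasibility is the primary measure, the section itself says that the study is not fully powered, and the next trial is to be designed from observed means and variability. This limits the severity, but it does not make the printed precision follow from the stated inputs.

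**Conclusion.** The point holds as a minor one. With 10 (8) per arm, the stated inputs give half-widths of about 0.66 (0.76) per arm, 0.47 (0.54) pooled and 0.94 (1.07) active minus sham, in SDs of the change score with a common variance. The stated 0.5 and 0.3 need three further conditions that the plan does not give: the raw-score SD as unit, overall meaning the pooled cohort, and a pre-post correlation of about 0.75 to 0.8 or an equivalent repeated-measures gain.

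On every basis checked, 0.3 is not the active-sham precision when each arm is at about 0.5; the implied value is about 0.45 to 0.71. These results assume equal arms and equal variances and, for the repeated-measures cases, equal correlations between visits. If 0.3 was meant for the pooled cohort, it describes a mean change and not a treatment effect, and the plan then states no active-sham precision. No decision rule depends on either number.

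**What to change.** Revise the precision sentences in the Sample Size Justification in one of two ways.

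- **Replace both figures**, for example: *With 10 (8) participants per arm and a common variance, the 95% CI half-width in SDs of the change score is about 0.66 (0.76) for each arm, 0.47 (0.54) for the pooled cohort and 0.94 (1.07) for active minus sham. These are simple change-score half-widths, without gain from covariates or repeated visits.*
- **Keep both figures**, but state that they are half-widths, name the SD unit, the model and the assumed correlation with its source, and reword the second quantity as the mean change in the pooled cohort.

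In either case, give the active-minus-sham half-width separately on the same basis: about 0.9 to 1.1 SD of change, or roughly 0.45 to 0.75 raw SD depending on the assumed model and correlation. Delete the word only.

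The cost is two or three sentences. Enrolment, design and analysis do not change; the one drawback is a less favourable stated precision.
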